8.21 Management of Hypertension

Hypertension is a known and potentially serious adverse event associated with lenvatinib treatment. Patients will be given a Blood Pressure Diary (Appendix III) on which to record their measurements. They should be instructed to check their blood pressure at least three times each week, and notify the treating physician if systolic BP ≥ 160 mmHg and/or diastolic BP ≥ 100 mmHg.

The following guidelines should be followed for the management of systolic BP ≥ 160 mmHg or diastolic BP ≥ 100 mmHg confirmed on repeat measurements after an hour:

Continue lenvatinib and institute antihypertensive therapy for subjects not already receiving this.

For those subjects already on antihypertensive medication, the dose of the current agent may be increased, if appropriate, or one or more agents of a different class of antihypertensive should be added.

If systolic BP ≥ 160 mmHg or diastolic BP ≥ 100 mmHg persists despite maximal antihypertensive therapy, then lenvatinib administration should be interrupted and restarted at a dose of 14 mg once daily (or one dose level reduction) when systolic BP ≤ 150 mmHg and diastolic BP ≤ 95 mmHg and the subject has been on a stable dose of antihypertensive medication for at least 48 hours.

If systolic BP ≥ 160 mmHg or diastolic BP ≥ 100 mmHg recurs on the 20-mg once daily dose despite optimal management of hypertension with antihypertensive medications (either by dose increase or the addition of a different class of antihypertensive), then lenvatinib administration should be interrupted and restarted at a dose of 14 mg once daily (one dose level reduction) only when systolic BP ≤ 150 mmHg and diastolic BP ≤ 95 mmHg and the subject has been on a stable dose of antihypertensive medication for at least 48 hours.

If systolic BP ≥ 160 mmHg or diastolic BP ≥ 100 mmHg recurs on the 14-mg once daily dose despite optimal management of hypertension with antihypertensive medications (either by dose increase or the addition of a different class of antihypertensive), then lenvatinib administration should be interrupted and restarted at a dose of 10 mg once daily (one dose level reduction) only when systolic BP ≤ 150 mmHg and diastolic BP ≤ 95 mmHg and the subject has been on a stable dose of antihypertensive medication for at least 48 hours.

If systolic BP ≥ 160 mmHg or diastolic BP ≥ 100 mmHg recurs on the 10-mg once daily dose despite optimal management of hypertension with antihypertensive medications (either by dose increase or the addition of a different class of antihypertensive), then lenvatinib administration should be interrupted and restarted at a dose of 4 mg once daily (one dose level reduction) only when systolic BP ≤ 150 mmHg and diastolic BP ≤ 95 mmHg and the subject has been on a stable dose of antihypertensive medication for at least 48 hours.

Additional dose reduction should be discussed with the ACCRU SAE

Coordinator (see protocol resource page).

The following guidelines should be followed for the management of Grade 4 hypertension (life-threatening consequences):

- Institute appropriate medical management
- Discontinue lenvatinib

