8.0 Dosage Modification Based on Adverse Events

Strictly follow the modifications in this table for the first **two** cycles, until individual treatment tolerance can be ascertained. Thereafter, these modifications should be regarded as guidelines to address side effects. If multiple adverse events are seen, administer dose based on greatest reduction required for any single adverse event observed. Reductions or increases apply to treatment given in the preceding cycle and are based on adverse events observed since the prior dose.

ALERT: *ADR reporting may be required for some adverse events (See Section 10)*

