8.1 Dose Levels (Based on Adverse Events in Tables 8.2 and 8.3)

Dose Level	Lenvatinib ^a	Pembrolizumab
0 ^b	20 mg orally once a day	200 mg IV every 21 days
-1	14 mg orally once a day	No dose reduction allowed
-2	10 mg orally once a day	No dose reduction allowed
-3	4 mg orally once a day	No dose reduction allowed

^a Once the dose has been reduced, it should not be increased at a later date.

^b Dose level 0 refers to the starting dose.

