8.2 Dose Modifications for **Lenvatinib**-Related Toxicities

Treatment-Related Toxicity^{a, b} including hepatic injury and venous thromboembolic events	Management	Dose Modification
Grade 1 and Tolerable Grade 2		
	Continue Treatment	No change
Intolerable Grade 2^c or Grade 3^{d, e}		
First occurrence	Hold until resolved to Grade 0-1 or baseline ^f	14 mg orally once a day
Second occurrence (same toxicity or new toxicity)	Hold until resolved to Grade 0-1 or baseline ^f	10 mg orally once a day
Third occurrence (same toxicity or new toxicity)	Hold until resolved to Grade 0-1 or baseline ^f	4 mg orally once a day
Fourth occurrence (same toxicity or new toxicity)	Hold until resolved to Grade 0-1 or baseline ^f	Contact ACCRU Quality Assurance Specialist
Grade 4^g: Discontinue Study Treatment		

NOTE: See CTCAE v4 for grading:

Collect all CTC grades of AEs, decreasing and increasing grade.

- a. A delay of study treatment for more than 28 days (due to treatment-related toxicities) will require a discussion with the ACCRU Quality Assurance Specialist before treatment can be resumed (see protocol resource page).
- b. Initiate optimal medical management for nausea, vomiting, and/or diarrhea prior to any study treatment, interruption, or dose reduction.
- c. Grade 2 toxicities will be determined to be tolerable or intolerable by both the subject and investigator. If Grade 2 toxicity is determined to be intolerable, the dose of study drug will be reduced with or without dose interruption. Interruption for Grade 3 toxicities is mandatory.
- d. Weight loss of any grade may not require dose reduction, but should be managed based on the judgment of the investigator. Subjects with weight loss requiring dose interruption and reduction do not need to return to baseline weight to restart lenvatinib. Based on the judgment of the investigator, subjects may be restarted at a lower dose of lenvatinib for weight loss. Consultation with a registered dietician may be helpful in managing weight loss.
- e. Not applicable to abnormal clinical laboratory values that are not clinically relevant based on the judgment of the investigator (e.g., ALT, AST, γ -GTP values $< 10 \times$ ULN, and Na).
- f. For hematology toxicities, restart treatment after toxicity resolves to Grade ≤ 2 .
- g. Excluding laboratory abnormalities judged to be non-life-threatening, in which case manage as Grade 3.

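### For lenvatinib-related hypertension graded 3, Section 8.21 and Table 8.2 give different hold, dose and restart instructions, and neither says which governs

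*Combined protocol and SAP*

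**What the plan says.** Section 8.21 sets out guidelines "for the management of systolic BP ≥ 160 mmHg or diastolic BP ≥ 100 mmHg confirmed on repeat measurements after an hour". The first step is "Continue lenvatinib and institute antihypertensive therapy for subjects not already receiving this"; patients already on such therapy have it increased or another class added. Only if the pressure "persists despite maximal antihypertensive therapy, then lenvatinib administration should be interrupted and restarted at a dose of 14 mg once daily" (or one dose level lower) is the drug withheld. Further steps to 14, 10 and 4 mg follow recurrence despite optimal management. Restart needs a pressure no higher than 150/95 and 48 hours on unchanged antihypertensives. Grade 4 hypertension is a separate tier, where the instruction is "Discontinue lenvatinib".

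Table 8.2 covers lenvatinib-related toxicity. For Grade 3, and for Grade 2 judged intolerable, it prescribes a hold to Grade 0-1 or baseline, then 14 mg after the first occurrence, 10 mg after the second and 4 mg after the third, counting the same or a new toxicity. Footnote c states: "Interruption for Grade 3 toxicities is mandatory". For Grade 4 it tells sites to stop study treatment. Section 8.1, footnote a, adds: "Once the dose has been reduced, it should not be increased at a later date".

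Section 8.0 makes the modifications strict for the first two cycles and guidance afterwards.

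**The concern.** A site that grades a patient's hypertension 3 finds two instructions. One keeps lenvatinib going at the current dose while antihypertensives are started or intensified. The other withholds it and lowers the dose for good.

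Hypertension is the most frequent lenvatinib toxicity that the protocol reports from the phase III trial (67.8%, any grade, Section 1.6), and Section 10.52 has it graded at every evaluation. Sites will therefore hold the CTCAE grade that leads them to Table 8.2. At stake is a consistent safety instruction for a foreseeable event and, secondarily, consistent lenvatinib exposure across sites in a single-arm trial whose Cohort 1 is judged against a lenvatinib-alone complete response rate.

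**Working it through.** No design figure is involved, so the check sets the two rules side by side and then follows the dose for one patient.

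| Item | Section 8.21 | Table 8.2 and footnotes |
|---|---|---|
| Trigger | Confirmed BP of at least 160 systolic or 100 diastolic, short of Grade 4 | Grade 3 lenvatinib-related toxicity |
| First action | Continue; start or intensify antihypertensives | Hold |
| Dose falls | Only on persistence or recurrence despite treatment | At the first occurrence |
| Restart | At most 150/95, after 48 h on stable medication | Grade 0-1 or baseline |
| Grade 4 | Lenvatinib stops | Study treatment stops |

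**Do the two rules overlap?** The documents cite CTCAE v4 but do not reproduce its blood pressure cut-offs. They are not needed to show some overlap. Section 8.21 applies to every confirmed reading at or above its threshold and sets apart only Grade 4. The grade immediately below 4 is 3, so hypertension at or above the threshold that is graded 3 falls under both rules. Whether a reading of exactly 160/100 is Grade 3 cannot be shown from the documents.

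**Is there a carve-out?** Footnote b puts optimal medical management ahead of interruption or reduction, but only for nausea, vomiting and diarrhea. Footnote d relaxes the rule for weight loss and footnote e for laboratory values that are not clinically relevant. Footnote f changes the restart grade for hematology, and footnote g concerns laboratory abnormalities at Grade 4. None names hypertension or points to 8.21, and 8.21 does not mention Table 8.2.

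**Dose trace, patient on 20 mg, first Grade 3 hypertension, no antihypertensive yet.**
- Section 8.21: 20 mg, no hold; 20 × 21 = 420 mg per cycle.
- Table 8.2: hold, then 14 mg; 14 × 21 = 294 mg per full cycle after restart.
- Difference: (420 − 294) / 420 = 30%, with no re-escalation.

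If Grade 3 hypertension then recurs despite optimal management, 8.21 moves this patient from 20 to 14 mg, and Table 8.2 moves the patient from 14 to 10 mg.

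**Restart.** Eligibility criterion 3.19a requires a pressure below 150/90 at screening. A patient at 150/95 meets the 8.21 restart condition but is above the screening limit. Under Table 8.2 the restart would then depend on whether that reading counts as Grade 0-1, which the documents do not settle.

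**Occurrence count.** Suppose the first Grade 3 hypertension is managed under 8.21 without a reduction, and an unrelated Grade 3 toxicity follows. If the hypertension counts, the new event is the second occurrence and leads to 10 mg. If it does not, the new event is the first and leads to 14 mg. The protocol does not say which.

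**Grade 4.** One passage stops lenvatinib and the other stops study treatment. Section 8.3 has its own pembrolizumab rules, including permanent discontinuation for Grade 4 drug-related toxicity and for any life-threatening event. It is linked to neither passage.

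**The case against.** The strongest reply is structural. Section 8.21 sits under 8.2 and has a complete algorithm of its own: dose ladder, restart condition and Grade 4 rule. Sections 8.23, 8.24 and 8.25 send sites to Table 8.2, and 8.21 does not. The table's heading names liver injury and venous thromboembolism, the subjects of 8.23 and 8.24, but not hypertension. A site could reasonably conclude that the specific section governs. That reading stands as plausible, but it remains an inference: the table's general scope takes in hypertension, footnote c is unqualified, and exceptions for other toxicities are written out.

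Several stronger readings are tempting and are not supported.
- A reader might infer that every reading of 160/100 triggers both rules. That needs a CTCAE cut-off that the documents do not give.
- A reader might infer that Section 8.0 settles the matter for Table 8.2 through "administer dose based on greatest reduction required for any single adverse event observed". That sentence addresses several adverse events in one patient, not two rules for one event. The strictness in 8.0 also lasts only two cycles.
- A reader might infer that patients receive contradictory instructions. They do not: the test schedule and 8.21 give the same threshold for notifying the team. The conflict is in the instructions to sites.
- A reader might turn 67.8% into 0.678 × 25, about 17 patients per cohort. That rate is any-grade, from a trial that the protocol links to a 24 mg start. Here the dose does not exceed 20 mg, and Cohort 2 patients are already on lenvatinib, with those who stopped it for toxicity excluded.

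**Conclusion.** The contradiction is real for lenvatinib-related hypertension graded 3. The instructions on hold, dose and restart differ, and no sentence ranks them. For a patient on 20 mg the first such event gives either 20 mg without a hold, or a hold and then 14 mg. The Grade 4 wording also needs reconciling, although 8.3 partly covers pembrolizumab.

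The conclusion rests on the text and on the ordering of the CTCAE grades, not on an assumed cut-off. How many patients would be affected cannot be derived. Nor can the size or direction of any effect on the comparison with the historical rate: dose variation between sites is possible but not shown. Power, sample size and the decision rules in Section 16 are unaffected. This is a safety clarification worth making, not a flaw in the statistical design.

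**What to change.** Reconcile Section 8.21 with Table 8.2 by adding a matching cross-reference in each that states:
- which passage governs hypertension below Grade 4;
- which restart criterion applies;
- whether an event managed under 8.21 counts toward the occurrence sequence in Table 8.2.

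Also align the Grade 4 wording in the two places on whether one drug or both stop, consistently with Section 8.3. The choice of clinical rule belongs to the sponsor; the documents need to state only one.

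The cost is a short protocol clarification and a notice to sites, with no extra patients or procedures.

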8.22 Management of Proteinuria

Regular assessment of proteinuria should be conducted as detailed in the Test Schedule (Section 4.0).

Guidelines for assessment and management of proteinuria:

A 24-hour urine collection for protein quantitation **is required** in the following situations:

- The first (initial) occurrence of 2+, 3+, or 4+ proteinuria on urine dipstick while on study drug
- A subsequent apparent increase in severity of urine dipstick proteinuria (from the prior measurement which was $\geq 2+$) occurring on the same lenvatinib dose level
- When there has been a lenvatinib dose reduction and on follow-up, the urine protein dipstick result is 2+, 3+, or 4+ (at the new dose level)

The 24-hour urine collection **is not required** in the following situations:

- Persistence of the same severity of proteinuria by urine dipstick at the same lenvatinib dose level (when a 24-hour urine collection has already been collected at that dose level)
- Subsequent occurrences of 2+, 3+, or 4+ proteinuria by urine dipstick when the subject has been off study drug

Grading of proteinuria should be performed according to CTCAE v4.03 (Appendix 3) BUT will be based on the 24-hour urine collection for total protein result, if a 24-hour urine was performed at that time point.

For subjects with lenvatinib-related toxicity, the dose reduction and/or interruption instructions provided in Table 2 of the study protocol should be followed.

8.23 Management of Hepatotoxicity

Regular monitoring of liver function tests (ALT, AST, bilirubin levels) should be conducted as clinically indicated. If signs/symptoms indicating liver injury occur, instructions contained in Table 8.2, “Dose Modifications for **Lenvatinib-Related Toxicities**” should be followed. Appropriate supportive care should be provided together with close monitoring. If hepatic failure occurs, lenvatinib must be discontinued.

8.24 Management of Venous and Arterial Thromboembolic Events

Subjects should be advised to pay attention to symptoms suggestive of venous thromboembolic events, which include acute onset of shortness of breath, dyspnea, chest pain, cough, hemoptysis, tachypnea, tachycardia, cyanosis, signs of deep vein thrombosis including lower-extremity swelling, and warmth to touch or tenderness. In case any of these symptoms appear, subjects should be instructed to report such symptoms promptly to the treating physician. If a venous thromboembolic event is confirmed, instructions contained in Table 8.2, “Dose Modifications for **Lenvatinib**-Related Toxicities” should be followed. Appropriate supportive care should be provided together with close monitoring.

If a subject experiences any arterial thromboembolic event, lenvatinib must be discontinued.

8.25 Management of Posterior Reversible Encephalopathy Syndrome

In clinical studies with lenvatinib, events of posterior reversible encephalopathy syndrome (PRES) were reported in less than 1% of lenvatinib-treated subjects. PRES is a neurological disorder, which can present with headache, seizure, lethargy, confusion, altered mental function, blindness, and other visual or neurological disturbances. Mild to severe hypertension may be present. MRI is necessary to confirm the diagnosis of PRES. Appropriate measures should be taken to control BP. In subjects with signs or symptoms of PRES, dose interruptions, dose adjustments, or discontinuation may be required as per instructions included in Table 8.2.

8.26 Management of Hypocalcemia

Serum calcium should be monitored per the Test Schedule (Section 4). Hypocalcemia should be treated per institutional guidelines (eg, using appropriate calcium, magnesium, and Vitamin D supplementation) until resolution.

8.27 Management of Myocarditis

8.27a LVEF normal/nonmalignant rhythm- Obtain cardiology consultation, review case with overall study PI, and consider 1 gram IV solumedrol daily for 3-5 days (consider mycophenolate vs IVIG vs cyclosporine vs plasmapheresis for persistent myocarditis).

8.27b LVEF reduced or patient is unstable- Obtain a cardiology consultation and review the case with overall study PI.

8.3 Dose Modifications for **Pembrolizumab**-Related Toxicities

CTCAE System/Organ/Class (SOC)	Adverse Event	Hold Treatment for Grade	Timing for Restarting Treatment	Treatment Discontinuation
Gastrointestinal Disorders	Diarrhea/Colitis	2-3	Toxicity resolves to Grade 0-1	Toxicity does not resolve within 12 weeks of last dose or inability to reduce corticosteroid to 10mg or less of prednisone or equivalent per day within 12 weeks.
		4	Permanently discontinue	Permanently discontinue
Endocrine Disorders	Other: Hypophysitis	2-4	Toxicity resolves to Grade 0-1. Therapy with pembrolizumab can be continued while endocrine replacement therapy is instituted.	Toxicity does not resolve within 12 weeks of last dose or inability to reduce corticosteroid to 10mg or less of prednisone or equivalent per day within 12 weeks.
Immune System Disorders	Infusion Reaction	3-4	Permanently discontinue	Permanently discontinue
Investigations	AST, ALT or Increased Bilirubin	2	Toxicity resolves to Grade 0-1	Toxicity does not resolve within 12 weeks of last dose.
		3-4	Permanently discontinue (see exception below) ^a	Permanently discontinue
Metabolism and Nutrition Disorders	Type 1 Diabetes Mellitus (if new onset) or Hyperglycemia	T1DM or 3-4	Hold pembrolizumab for new onset Type 1 diabetes mellitus or Grade 3-4 hyperglycemia associated with evidence of beta cell failure.	Resume pembrolizumab when subject is clinically and metabolically stable.
	Hypercalcemia	3-4	Toxicity resolves to Grade 0-1	Resume pembrolizumab when subject is clinically and metabolically stable.

CTCAE System/Organ/Class (SOC)	Adverse Event	Hold Treatment for Grade	Timing for Restarting Treatment	Treatment Discontinuation
Renal and urinary disorders	Renal Failure or Nephritis	2	Toxicity resolves to Grade 0-1	Toxicity does not resolve within 12 weeks of last dose or inability to reduce corticosteroid to 10mg or less of prednisone or equivalent per day within 12 weeks.
		3-4	Permanently discontinue	Permanently discontinue
Respiratory, thoracic and mediastinal disorders	Pneumonitis	2	Toxicity resolves to Grade 0-1	Toxicity does not resolve within 12 weeks of last dose or inability to reduce corticosteroid to 10mg or less of prednisone or equivalent per day within 12 weeks.
		3-4	Permanently discontinue	Permanently discontinue
Myocarditis	Grade 1 or 2	Withhold	Based on severity of AE administer corticosteroids	Ensure adequate evaluation to confirm etiology and/or exclude other causes
	Grade 3 or 4	Permanently Discontinue		
	All Other Drug-Related Toxicity ^b	3 or Severe	Toxicity resolves to Grade 0-1	Toxicity does not resolve within 12 weeks of last dose or inability to reduce corticosteroid to 10mg or less of prednisone or equivalent per day within 12 weeks.
		4	Permanently discontinue	Permanently discontinue

NOTE: Permanently discontinue for any severe or Grade 3 drug-related AE that recurs or any life-threatening event.

- a. For subjects with liver metastasis who begin treatment with Grade 2 AST or ALT, if AST or ALT increases by greater than or equal to 50% relative to baseline and lasts for at least 1 week then subjects should be discontinued.
- b. Subjects with intolerable or persistent Grade 2 drug-related AE may hold study medication at physician discretion. Permanently discontinue study drug for persistent Grade 2 adverse reactions for which treatment with study drug has been held, that do not recover to Grade 0-1 within 12 weeks of the last dose.

8.4 Treatment Guidelines for Subjects Who Experience an Infusion Reaction Associated with the Administration of **Pembrolizumab**

Infusion Reaction Treatment Guidelines for Pembrolizumab		
CTCAE Grade	Treatment	Premedication at subsequent dosing
Grade 1 Mild reaction; infusion interruption not indicated; intervention not indicated	Increase monitoring of vital signs as medically indicated until the subject is deemed medically stable in the opinion of the investigator.	None
Grade 2 Requires infusion interruption but responds promptly to symptomatic treatment (e.g., antihistamines, NSAIDs, narcotics, IV fluids); prophylactic medications indicated for ≤ 24 hours	
Stop infusion and monitor symptoms. Additional appropriate medical therapy may include but is not limited to:
 
 • IV fluids • Antihistamines • NSAIDs • Acetaminophen • Narcotics 
Increase monitoring of vital signs as medically indicated until the subject is deemed medically stable in the opinion of the investigator.
 
If symptoms resolve within one hour of stopping drug infusion, the infusion may be restarted at 50% of the original infusion rate (e.g., from 100 mL/h to 50 mL/h). Otherwise dosing will be held until symptoms resolve and the subject should be premedicated for the next scheduled dose.
 
Subjects who develop Grade 2 toxicity despite adequate premedication should be permanently discontinued from further study treatment administration.
	
Subject may be premedicated 1.5h (± 30 minutes) prior to infusion of pembrolizumab with:
 
 • Diphenhydramine 50 mg orally (or equivalent dose of antihistamine). • Acetaminophen 500-1000 mg orally (or equivalent dose of antipyretic).

Infusion Reaction Treatment Guidelines for Pembrolizumab		
CTCAE Grade	Treatment	Premedication at subsequent dosing
Grades 3 or 4 Grade 3: Prolonged (i.e., not rapidly responsive to symptomatic medication and/or brief interruption of infusion); recurrence of symptoms following initial improvement; hospitalization indicated for other clinical sequelae (e.g., renal impairment, pulmonary infiltrates) Grade 4: Life-threatening; pressor or ventilator support indicated	Stop Infusion. Additional appropriate medical therapy may include but is not limited to: 
 • IV fluids • Antihistamines • NSAIDs • Acetaminophen • Narcotics • Oxygen • Pressors • Corticosteroids • Epinephrine Increase monitoring of vital signs as medically indicated until the subject is deemed medically stable in the opinion of the investigator. Hospitalization may be indicated. Subject is permanently discontinued from further study treatment administration.	No subsequent dosing.
Appropriate resuscitation equipment should be available in the room and a physician readily available during the period of drug administration.		

Dosing interruptions are permitted in the case of medical/surgical events or logistical reasons not related to study therapy (e.g., elective surgery, unrelated medical events, subject vacation, and/or holidays). Subjects should be placed back on study treatment within 3 weeks of the scheduled interruption, unless otherwise discussed with the Sponsor. The reason for interruption should be documented in the subject's study record.

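### Table 8.3 gives two instructions for a life-threatening endocrine or metabolic event: its NOTE stops pembrolizumab permanently, while the hypophysitis, T1DM/hyperglycemia and hypercalcemia rows hold and restart it

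*Combined protocol and SAP*

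**What the plan says.** All of the text at issue is in Section 8 of the combined protocol and SAP.

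- **NOTE under the Section 8.3 table:** "Permanently discontinue for any severe or Grade 3 drug-related AE that recurs or any life-threatening event". It names no exempt event.
- **Hypophysitis row:** the event and hold grades are "Other: Hypophysitis 2-4". The restart column says "Toxicity resolves to Grade 0-1. Therapy with pembrolizumab can be continued while endocrine replacement therapy is instituted". The discontinuation column covers only failure to resolve, or to taper corticosteroids, within 12 weeks.
- **Type 1 diabetes/hyperglycemia row:** "Hold pembrolizumab for new onset Type 1 diabetes mellitus or Grade 3-4 hyperglycemia associated with evidence of beta cell failure". The discontinuation column holds a restart instruction: "Resume pembrolizumab when subject is clinically and metabolically stable".
- **Hypercalcemia row:** "Hypercalcemia 3-4 Toxicity resolves to Grade 0-1", with the same restart instruction in the discontinuation column.

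Section 8.0 makes the modifications strict for the first two cycles and guidelines after that. It does not rank a note against a row. Section 8.4 describes the top grade of infusion reaction as "Grade 4: Life-threatening; pressor or ventilator support indicated", and Section 8.21 likewise ties Grade 4 hypertension to life-threatening consequences.

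**The concern.** If a patient has a life-threatening event that falls in one of these three rows, the row leads back to pembrolizumab and the NOTE rules it out for good. Two sites could each follow the table in good faith and act in opposite ways. What is at stake is re-exposure to the drug after a life-threatening event, and so patient safety and uniform conduct across sites. It also decides whether the patient goes on receiving the combination under study.

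**Working it through.** No figure in the plan depends on this point, so the check is a row-by-row reading, followed by simple arithmetic on how often the conflict could arise.

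**Step 1. Each row of the Section 8.3 table that reaches Grade 4, set against the NOTE.**

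| Row | Instruction at Grade 4 | Agrees with NOTE if life-threatening? |
|---|---|---|
| Diarrhea/colitis | permanent stop | yes |
| Infusion reaction | permanent stop | yes |
| AST, ALT or bilirubin | permanent stop, with an exception marked by footnote a | yes, apart from the marked exception |
| Renal failure or nephritis | permanent stop | yes |
| Pneumonitis | permanent stop | yes |
| Myocarditis | permanent stop | yes |
| All other drug-related toxicity | permanent stop | yes |
| Hypophysitis | hold, restart | no |
| T1DM/hyperglycemia with beta cell failure | hold, restart | no |
| Hypercalcemia | hold, restart | no |

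Ten rows reach Grade 4. Seven follow the NOTE and 10 - 7 = 3 do not.

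**Step 2. Is there a precedence rule or an exemption?** Sections 8.0 to 8.4, 9.8, 9.9 and 9.9a contain none that covers these rows. Section 9.9 gives steroid and hormone management for Grade 3-4 hypophysitis. Section 9.8 gives insulin and work-up for new-onset T1DM, and includes ketoacidosis there. Neither says whether pembrolizumab stops or resumes.

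**Step 3. When is a Grade 4 event life-threatening?** The documents make that link explicitly for infusion reactions (8.4) and hypertension (8.21). Footnote g of the lenvatinib table (8.2) accepts that some Grade 4 laboratory abnormalities are not life-threatening. It does not apply to pembrolizumab, but it shows that the protocol does not treat the two terms as always the same. It follows that:

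- Grade 4 hypophysitis is not a laboratory value, so that distinction offers no way round the conflict.
- For hyperglycemia and hypercalcemia the conflict is present when the event is life-threatening (ketoacidosis of that severity, for example) and arguable when Grade 4 is only a laboratory result.

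**Step 4. How often?** Section 15.27 lists hypophysitis, type 1 diabetes and hypercalcemia at 0.1% to under 1% each. Maximum accrual is 60 (Section 16.21). Expected cases of each event = 60 × rate:

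- lower end: 60 × 0.001 = 0.06
- upper end: 60 × 0.01 = 0.6, so under 0.6

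For the three together: 3 × 0.06 = 0.18 to under 3 × 0.6 = 1.8. These are cases of any grade, so life-threatening cases would be fewer. The documents give no rate by grade, for the combination, or for hyperglycemia apart from T1DM.

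**Step 5. How long are the rules strict?** Two cycles of 21 days: 2 × 21 = 42 days.

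**Step 6. What differs for one patient?** Planned treatment is 19 cycles (Section 13.4), and the test schedule runs to Cycle 35 for those who extend. For an event after the second infusion, the readings differ between no further pembrolizumab and up to 19 - 2 = 17 more infusions, or 35 - 2 = 33 with extension.

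**The case against.** The best reply is that a specific row overrides a general note, so the three rows are exceptions to it. That is a possible reading, but the protocol does not state it. In the same table the AST/ALT/bilirubin row has an exception that is flagged and footnoted, and these three rows carry no such flag. Someone following the NOTE literally would also be following the protocol.

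Three parts of the case against do stand, and they limit the point. Grade 4 and life-threatening are not interchangeable throughout, so the metabolic rows conflict with the NOTE only in part. After the first two cycles the modifications are guidelines, so the clash between binding rules is confined to about six weeks; after that it is conflicting guidance. And the trial may well see no such case.

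A reader might infer more than the text supports:

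- **That the three rows also conflict with the NOTE at a recurrent Grade 3.** They do not. The rows are silent on recurrence and the NOTE adds to them, so both can be followed. Colitis and the all-other row at Grade 3 are in the same position.
- **That the hypophysitis row contradicts itself by holding the drug and also allowing it.** The sentence "Therapy with pembrolizumab can be continued while endocrine replacement therapy is instituted" stands in the restart column, after the resolution criterion. It can be read as saying that ongoing hormone replacement does not bar a restart. It is unclear, but not a definite contradiction.
- **That the choice moves the patient to a different scan schedule through Observation.** Section 13.3 applies to patients who go off protocol treatment, and the documents do not clearly say that stopping pembrolizumab alone counts. After week 18 on-treatment imaging is every 12 weeks in any case (12 × 7 = 84 days), the same interval as Observation.

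**Conclusion.** The inconsistency is real and should be corrected. For a life-threatening event in any of three of the ten Grade 4 rows, the Section 8.3 table gives opposite instructions and no rule for choosing between them. It is plain for Grade 4 hypophysitis, and conditional on the event being life-threatening for hyperglycemia and hypercalcemia.

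Its expected frequency is low: 0.06 to under 0.6 cases of each listed event at any grade among 60 patients, assuming that the Section 15.27 rates carry over to this combination and population. Its importance lies in the consequence for the individual patient. No primary endpoint, decision rule or analysis has been shown to change. The conclusion assumes that the NOTE applies to the whole table, as its unrestricted wording indicates.

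**What to change.** Amend Section 8.3 so that the NOTE and the hypophysitis, T1DM/hyperglycemia and hypercalcemia rows give one instruction for a life-threatening event. This can be done by naming in the NOTE any row that is exempt, or by changing the rows to agree with it. For the two metabolic rows, say whether a Grade 4 laboratory value without life-threatening consequences falls under the NOTE. Say also whether the hypophysitis sentence on continuing during endocrine replacement applies only once the hold has resolved. Which clinical rule stands is for the sponsor's clinicians, and this review does not propose one.

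The cost is a wording amendment to one table. It changes no sample size, visit or analysis.
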